#### **4.3.3 Criteria for withdrawal**

All subjects discontinuing treatment with study medication for any reason should taper off medication as described in Section 4.4.1. Whenever possible, these cases should be discussed with the medical monitor prior to withdrawing the subject from the study. All subjects who withdraw from the study due to an AE must be followed until resolution of the event or until the event is considered stable. The following criteria for subject withdrawal from SP848 are outlined below. Additional discontinuation criteria for potential drug-induced liver injury (PDILI) are presented in Section 4.3.3.1.

Participation in this study **must** be discontinued for any of the following reasons:

1. Intolerable AEs, including clinically relevant abnormal laboratory findings that, in the opinion of the investigator, preclude further participation in the study
2. The request of the Sponsor or a Regulatory Agency

3. Subject achieves menarche during the study and does not practice an acceptable method of contraception for the duration of the study (unless sexually abstinent).
4. Subject becomes pregnant, as evidenced by a positive pregnancy test.
5. Subject has a corrected QT interval (QTc) of greater than or equal to 500ms as confirmed by a cardiologist overread on any ECG.
6. Subject develops a second-degree atrioventricular (AV) block while awake or develops a third-degree AV block at any time.
7. Subject is unwilling or unable to continue, or the caregiver/parent/legal guardian is unwilling or unable to allow the subject to continue in the study.
8. Investigator's decision that withdrawal from further participation would be in the subject's best interest.
9. Subject experiences convulsive status epilepticus (if none had occurred prior to study entry) and is compliant with study treatment
11. For subject who did not complete a C-SSRS at Screening, subject has a lifetime history (prior to study entry or since study start) of suicide attempt (including an actual attempt, interrupted attempt, or aborted attempt) of the screening version of the C-SSRS. The investigator must withdraw the subject from the study and immediately refer the subject to a Mental Healthcare Professional.
12. For all subjects  $\geq 6$  years of age, regardless of whether or not a C-SSRS was completed at Screening, subject has actual suicidal ideation as indicated by a positive response ("Yes") to either Question 4 or Question 5 of the "since last visit" version of the C-SSRS. The subject should be referred immediately to a Mental Healthcare Professional and must be withdrawn from the study.

Participation in this study **may** be discontinued for any of the following reasons:

1. Any clinically relevant change in medical or psychiatric condition (if in the opinion of the investigator, the condition warrants discontinuation from the study).
2. Subject requires a medication that is not permitted by the protocol.
3. Subject and/or delegated caregiver is unable to manage the completion of the diary or is noncompliant with study procedures or medication, in the opinion of the investigator.
5. For subject who did not complete a C-SSRS at Screening, subject had actual suicidal ideation in the past 6 months as indicated by a positive response ("Yes") to either Question 4 or Question 5 of the screening version of the C-SSRS. The investigator must immediately refer the subject to a Mental Healthcare Professional and use clinical judgment as to whether to withdraw the patient from the study.

If a subject from SP848 enrolls in EP0060 and either withdraws consent solely due to route of LCM administration (iv) or if the subject requires more than 10 iv LCM infusions, the subject may be allowed to return to SP848 after discussion with and agreement from the Medical Monitor. If a subject from SP848 is advised to withdraw from the SP848 after participation in EP0060, the subject will be required to return to the SP848 to complete the required ETV and Safety Follow-up assessments.

Investigators should attempt to obtain information on subjects in the case of withdrawal. For subjects considered as lost to follow up, the investigator should make efforts (at least 1 phone call and 1 written message to the subject), and document his/her efforts (date and summary of the phone call and copy of the written message in the source documents), to complete the final evaluation. All results of these evaluations and observations, together with a narrative description of the reason(s) for removing the subject, must be recorded in the source documents. The eCRF must document the primary reason for withdrawal.

Investigators should contact the Medical Monitor, whenever possible, to discuss the withdrawal of a subject in advance.

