#### **4.3.3.1 Potential drug-induced liver injury IMP discontinuation criteria**

Subjects with potential drug-induced liver injury (PDILI) must be assessed to determine if IMP must be immediately and permanently discontinued. In addition, all concomitant medications and herbal supplements that are not medically necessary should also be discontinued.

The PDILI criteria below require immediate and permanent discontinuation of IMP:

- Subjects with either of the following:
  - ALT or AST  $\geq 5\times$ ULN
  - ALT or AST  $\geq 3\times$ ULN and coexisting total bilirubin  $\geq 2\times$ ULN
- Subjects with ALT or AST  $\geq 3\times$ ULN who exhibit temporally associated symptoms of hepatitis or hypersensitivity. Hepatitis symptoms include fatigue, nausea, vomiting, and right upper quadrant pain or tenderness. Hypersensitivity symptoms include fever (without clear alternative cause), rash, or eosinophilia (ie,  $>5\%$ ).

The PDILI criterion below requires discussion with the Medical Monitor to decide whether the subject is allowed to continue on IMP.

- Subjects with ALT or AST  $\geq 3\times$ ULN (and  $\geq 2\times$  Baseline) and  $<5\times$ ULN, total bilirubin  $<2\times$ ULN, and no eosinophilia (ie,  $\leq 5\%$ ), with no fever, rash, or symptoms of hepatitis (eg, fatigue, nausea, vomiting, right upper quadrant pain or tenderness).

Evaluation of PDILI must be initiated as described in [Section 8.3.2](#). If subjects are unable to comply with the applicable monitoring schedule, IMP must be discontinued immediately.

Investigators should attempt to obtain information on subjects in the case of IMP discontinuation to complete the final evaluation. Subjects with PDILI should not be withdrawn from the study until investigation and monitoring are complete. All results of these evaluations and observations, as well as the reason(s) for IMP discontinuation and subject withdrawal (if applicable), must be recorded in the source documents. The eCRF must document the primary reason for IMP discontinuation.

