Subjects enrolling from SP847 will have the option of remaining on the oral solution formulation of LCM or switching to the commercial tablet formulation, if feasible. Consideration of the current LCM milligram dose in the oral solution (syrup) should occur if/when transitioning to the tablet formulation. In cases where the LCM dose received with the oral solution (syrup) is not supported by the tablet strengths available in SP848 (50mg and 100mg), a clinical decision must

be made by the investigator or other study physician to either increase or decrease the LCM dose to the next multiple of 100mg with a maximum permitted dose of 600mg/day.

Subjects achieving a dose of LCM  $\geq$ 6mg/kg/day (oral solution [syrup]) or  $\geq$ 300mg/day (tablet) who withdraw during the study should taper off study medication. It is recommended that the dose be tapered gradually in weekly decrements of 4mg/kg/day (oral solution [syrup]) or 200mg/day (tablet) (see tables below). A slower taper of 2mg/kg/day (oral solution [syrup]) or 100mg/day (tablet) is permitted, if medically necessary. In case of an emergency, a faster taper is permitted after discussion with the medical monitor, whenever possible.

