#### **Recommended LCM dose reduction (taper) for oral solution (syrup) formulation**

Maximum LCM dose achieved a	Taper schedule		
	Week 1	Week 2	Week 3
12mg/kg/day (6mg/kg bid)	8mg/kg/day (4mg/kg bid)	4mg/kg/day (2mg/kg bid)	0
10mg/kg/day (5mg/kg bid)	6mg/kg/day (3mg/kg bid)	2mg/kg/day (1mg/kg bid)	0
8mg/kg/day (4mg/kg bid)	4mg/kg/day (2mg/kg bid)	0	–
6mg/kg/day (3mg/kg bid)	2mg/kg/day (1mg/kg bid)	0	–
4mg/kg/day (2mg/kg bid)	0	–	–

bid=twice daily; LCM=lacosamide

a Maximum LCM dose achieved is based upon the maximum recommended dose in SP847.

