#### **Recommended LCM dose reduction (taper) for tablet formulation**

Maximum LCM dose achieved a	Taper schedule		
	Week 1	Week 2	Week 3
600mg/day (300mg bid)	400mg/day (200mg bid)	200mg/day (100mg bid)	0
500mg/day (250mg bid)	300mg/day (150mg bid)	100mg/day (50mg bid)	0
400mg/day (200mg bid)	200mg/day (100mg bid)	0	–
300mg/day (150mg bid)	100mg/day (50mg bid)	0	–
200mg/day (100mg bid)	0	–	–

bid=twice daily; LCM=lacosamide

a Maximum LCM dose achieved is based upon the maximum recommended dose in SP847.

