### 8.3.2      Liver function tests and evaluation of PDILI

The PDILI IMP discontinuation criteria for this study are provided in [Section 4.3.3.1](#) with the accompanying required follow-up investigation and monitoring detailed below. All PDILI events must be reported as an AE and reported to the study site and sponsor within 24 hours of learning of their occurrence. Any PDILI event that meets the criterion for potential Hy's Law must be reported as an AE of special interest (see [Section 8.2.2](#)), and, if applicable, also reported as an SAE (see [Section 8.2.1](#)).

Evaluation of PDILI consists of the diagnostic testing and continued monitoring included in [Table 8–1](#) (specific tests dependent on laboratory results and corresponding symptoms) and consultation with a local hepatologist (if applicable; discussed in [Section 8.3.2.1](#)). The local hepatologist is the expert usually consulted by the treating physician for assessment and management of potential hepatic disease. This would usually be a hepatologist, but may be a gastroenterologist. Additional investigation and monitoring may be required and adapted based on the diagnosis after the cause of the liver injury/abnormality is confirmed (details in [Section 8.3.2.4](#)).

The results of all monitoring, including laboratory testing and other testing, should be made available to the study site and sponsor.

All initial tests resulting in abnormal hepatic laboratory values need to be repeated, but appropriate medical action must not be delayed waiting for the repeat result.

If tests are done locally for more rapid results, a concurrent sample should also be sent to the central laboratory whenever possible. Medical care decisions are to be made initially using the most rapidly available results and a conservative approach must be taken if the results from the 2 laboratory tests are significantly different. Data from the local and central laboratory are to be recorded on the applicable eCRF pages.

When IMP is discontinued, all concomitant medications and herbal supplements that are not medically necessary should also be discontinued. In these cases, the investigator should also consider dose reduction for medically necessary concomitant medication and consider changing any medically required concomitant medication known to be hepatotoxic to a suitable alternative.

When IMP is stopped due to PDILI (as described in Section 4.3.3.1), IMP must be permanently discontinued.

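### Section 4.3.3 tells every subject who stops lacosamide to taper, with no exception for the liver-injury criteria that require an immediate and permanent stop

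*Protocol*

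**What the plan says.** The general rule opens Section 4.3.3 (Criteria for withdrawal): "All subjects discontinuing treatment with study medication for any reason should taper off medication as described in Section 4.4.1". Its trigger is stopping the drug, whatever the reason, and no exception follows. Later in the paragraph the reader is told: "Additional discontinuation criteria for potential drug-induced liver injury (PDILI) are presented in Section 4.3.3.1".

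Section 4.3.3.1 states: "The PDILI criteria below require immediate and permanent discontinuation of IMP". The criteria are ALT or AST at least 5xULN; ALT or AST at least 3xULN with total bilirubin at least 2xULN; and ALT or AST at least 3xULN with symptoms of hepatitis or hypersensitivity. A subject who cannot keep to the monitoring schedule must also stop at once. Table 8-1 gives the same action, and Section 8.3.2 adds: "When IMP is stopped due to PDILI (as described in Section 4.3.3.1), IMP must be permanently discontinued". On study status, 4.3.3.1 says: "Subjects with PDILI should not be withdrawn from the study until investigation and monitoring are complete".

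The taper itself is in Section 4.4.1.3. It concerns subjects who have reached 6 mg/kg/day (syrup) or 300 mg/day (tablet) and "who withdraw during the study should taper off study medication". Two tables set out the weekly steps, one titled "Recommended LCM dose reduction (taper) for oral solution (syrup) formulation" and the other "Recommended LCM dose reduction (taper) for tablet formulation". Section 5.17 (Early Termination Visit) repeats the gradual taper for subjects who withdraw early and stop lacosamide, and provides for taper drug to be dispensed from the same dose thresholds.

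**The concern.** An investigator stopping the drug because of a liver signal will open Section 4.3.3, and the first instruction there is to taper. The next subsection says to stop at once. A schedule lasting one or two weeks is not an immediate stop, so for subjects at or above the taper thresholds the protocol gives two incompatible instructions for one event and does not say which prevails. Because tapering an antiepileptic drug is clinically plausible, the general sentence does not announce itself as a slip.

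What is at stake is the conduct of a safety rule in children: continued dosing, after a serious liver signal, with a drug the protocol says must stop. It is not a question of estimation or inference.

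**Working it through.** The plan states no figure on this point, so there is none to reproduce. The check sets the texts side by side and then works out the extra drug from the protocol's taper tables.

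**Does the 4.3.3 sentence reach a PDILI stop?** Yes, on its words. It applies to anyone discontinuing study medication and is not limited to subjects leaving the study. The paragraph itself lists PDILI among the discontinuation criteria.

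**Does any text reconcile the two rules?** The places to look are 4.3.3, 4.3.3.1, 4.4.1.3, 5.17 and 8.3.2 with its subsections.

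- 4.3.3 points to 4.3.3.1 for added criteria but does not waive the taper.
- 4.3.3.1, 8.3.2 and Table 8-1 require the stop and do not mention the taper.
- 4.4.1.3 allows a faster taper in an emergency. That is still a taper, and PDILI is not named.
- 5.17 says some early withdrawals may not need a taper, depending on the treatment option chosen. Subjects who discontinue lacosamide are still told to taper gradually, again with no PDILI exception.

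By contrast, the pregnancy text in 8.1.6 offers a choice between stopping immediately and down-titrating. The PDILI text offers no such choice, so its plain meaning is that dosing ends.

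**Where do the rules collide?** At 4 mg/kg/day (syrup) or 200 mg/day (tablet) the taper tables go straight to 0, so nothing conflicts. The collision starts at 6 mg/kg/day or 300 mg/day.

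**How much drug is involved if the recommended taper is followed?** Inputs: the steps in the two tables, 7 days per step, dosing twice daily, and a subject on the tabulated dose when the criterion is met. Days = 7 × number of non-zero steps. Dosing times = 2 × days. Extra drug = 7 × sum of the stepped daily doses. Dividing by the prior daily dose gives the equivalent in days at that dose.

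| Prior dose | Steps | Days | Dosing times | Extra drug | Equivalent days |
|---|---|---|---|---|---|
| 12 mg/kg/day | 8, 4, 0 | 14 | 28 | 7 × (8 + 4) = 84 mg/kg | 84/12 = 7.0 |
| 10 mg/kg/day | 6, 2, 0 | 14 | 28 | 7 × (6 + 2) = 56 mg/kg | 56/10 = 5.6 |
| 8 mg/kg/day | 4, 0 | 7 | 14 | 7 × 4 = 28 mg/kg | 28/8 = 3.5 |
| 6 mg/kg/day | 2, 0 | 7 | 14 | 7 × 2 = 14 mg/kg | 14/6 = 2.3 |
| 4 mg/kg/day | 0 | 0 | 0 | 0 | 0 |
| 600 mg/day | 400, 200, 0 | 14 | 28 | 7 × (400 + 200) = 4200 mg | 4200/600 = 7.0 |
| 500 mg/day | 300, 100, 0 | 14 | 28 | 7 × (300 + 100) = 2800 mg | 2800/500 = 5.6 |
| 400 mg/day | 200, 0 | 7 | 14 | 7 × 200 = 1400 mg | 1400/400 = 3.5 |
| 300 mg/day | 100, 0 | 7 | 14 | 7 × 100 = 700 mg | 700/300 = 2.3 |
| 200 mg/day | 0 | 0 | 0 | 0 | 0 |

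Under 4.3.3.1 the intended figure is 0 in every row. The slower taper that 4.4.1.3 permits when medically necessary would take longer: from 12 mg/kg/day, in steps of 2 mg/kg/day, it runs 10, 8, 6, 4, 2, 0, which is 5 × 7 = 35 days. An emergency faster taper would be shorter than the tabulated schedule.

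**The case against.** The strongest reply is that the protocol already shows which rule wins. The taper sentence is advisory, whereas the PDILI text is mandatory, specific and repeated in 4.3.3.1, 8.3.2 and Table 8-1. Section 8.3.2.2 sends the reader to 4.3.3.1 and Table 8-1 for the action to take, not to the taper. Section 8.3.2.1 requires the Medical Monitor to be notified within 24 hours and the subject to be discussed as soon as possible. All of this stands and makes an error unlikely. It does not make the text consistent, because the reader must supply the rule that the specific overrides the general.

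A second reply is that the taper text in 4.4.1.3 covers subjects who withdraw, while PDILI subjects stay in the study until monitoring is complete. That is correct for 4.4.1.3, and for the same reason 5.17 bites less directly. It does not rescue 4.3.3, whose own trigger is discontinuing treatment and which brings in the Section 4.4.1 taper on that wider basis.

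A reader might infer that children meeting a liver stop criterion would in practice be kept on lacosamide for up to two weeks. The documents do not support that: the figures above show the size if the sentence were followed, not how likely that is. Nor do they support an inference that the study's safety or efficacy results are compromised, since no endpoint, analysis set or sample size depends on this wording.

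**Conclusion.** The contradiction is real and lies in the current text. The opening sentence of 4.3.3 is wrong as written for subjects on at least 6 mg/kg/day or 300 mg/day who meet a PDILI stop criterion. Section 5.17 carries the same omission with less direct force. The mandatory PDILI rule is clear and should govern; the general sentence is what needs correcting.

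Following the recommended taper would mean 7 to 14 days of dosing that should not occur. This rests on the tabulated steps of 7 days each and on the subject being at the tabulated dose when the criterion is met. Confidence is high as to the wording; the practical consequence is conditional and improbable. It is worth correcting because it concerns a paediatric stopping rule and the correction costs very little.

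**What to change.** Add an exception to the opening sentence of 4.3.3: *except where Section 4.3.3.1 requires immediate discontinuation of IMP, in which case LCM is stopped without the Section 4.4.1 taper*. Cross-reference the exception in 4.4.1.3 and in 5.17, including the item there on dispensing taper drug.

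The cost is one clause and two cross-references at the next amendment. No new procedure follows, because the immediate stop and the Medical Monitor discussion are already required. Seizure management after an abrupt stop can be covered in the discussion that 8.3.2.1 already requires; removing the contradiction does not call for a further requirement.

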#### **4.3.2 Exclusion criteria**

**Subjects are not permitted to enroll in the study if any of the following criteria are met:**

1. Subject is receiving any investigational drugs or using any experimental devices in addition to LCM.
3. Subject  $\geq 6$  years of age has a lifetime history of suicide attempt (including an actual attempt, interrupted attempt, or aborted attempt), or has suicidal ideation in the past 6 months as indicated by a positive response (“Yes”) to either Question 4 or Question 5 of the Columbia-Suicide Severity Rating Scale (C-SSRS) at Screening.

**Subjects who have participated in SP847 or other LCM pediatric clinical studies in epilepsy are not permitted to enroll in the study if any of the following criteria are met:**

2. Subject meets either of the following:
  - a. Withdrawal criteria for the primary study (with the exception of subjects who discontinued due to a dose reduction or status epilepticus). For subjects entering from EP0060, if the subject (or legal guardian) withdraws consent solely due to route of LCM administration (iv) or if the subject requires more than 10 iv LCM infusions, the subject may be allowed to participant in SP848 after discussion with and agreement from the Medical Monitor.
  - b. Ongoing serious AE (SAE).

**Subjects who enroll directly into SP848 without previous participation in a LCM clinical study are not permitted to enroll in the study if any of the following criteria are met:**

4. Subject has ever received LCM.
5. Subject has any medical or psychiatric condition that, in the opinion of the investigator, could jeopardize or would compromise the subject's ability to participate in this study.
6. Subject has a medical condition that could reasonably be expected to interfere with drug absorption, distribution, metabolism, or excretion.
7. Subject has a known hypersensitivity to any component of the investigational medicinal product.
8. Subject is a female of childbearing potential and does not practice an acceptable method of contraception for the duration of the study.
  - Medically acceptable contraceptive method includes oral or depot contraceptive treatment with at least 30 $\mu$ g ethinylestradiol per intake (or 50 $\mu$ g if associated with carbamazepine [or other strong enzyme inducers, eg, phenobarbital, primidone, oxcarbazepine]) which must be used in conjunction with a barrier method. Sexual abstinence is also an acceptable method of contraception.

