The informed consent process for SP848 will be conducted at Visit 1 for subjects who have not previously been through the informed consent process at the Screening Visit (ie, subjects enrolling from SP847 or other LCM pediatric clinical studies in epilepsy for whom Visit 1 is the first study visit in SP848). Prior to the conduct of any study-related procedures, a complete explanation (both verbally and written) of the nature and purpose of the study will be given to the subject (when possible or as required according to local IRBs/IECs) and the subject's parent/legal guardian by the investigator (or designee). The subject's parent/legal guardian will be requested to sign and date the IRB/IEC-approved Informed Consent Form. When possible, or as required by local IRB/IEC, the subject will be requested to give assent to participate in the study.

Each subject's eligibility will be determined on the basis of the inclusion/exclusion criteria and the results of the following assessments (applicable only for subjects for whom Visit 1 is the first clinic visit for SP848), and a complete medical history update will be obtained. If available, the data for the following assessments will be taken from the last assessment during SP847 (or other primary study, as applicable):

- Concomitant medications assessment
- Concomitant AEDs assessment
- Complete physical examination
- Complete neurological examination
- 12-lead ECG (2 interpretable recordings approximately 20 to 30 minutes apart prior to vital signs assessment but 30 minutes to 1 hour after the administration of LCM)
- Vital signs assessment (blood pressure and pulse)
- Body weight and height assessment
- Blood sample for clinical chemistry, hematology, and endocrinology
- Blood sample for LCM and concomitant AED plasma concentrations
- Urine sample for urinalysis
- Serum pregnancy test for female subjects of childbearing potential
- Tanner Stage assessment (if applicable)
- Clinical Global Impression of Change
- Caregiver Global Impression of Change
- C-SSRS

- Achenbach CBCL to be completed by the parent(s)/legal representative(s) (CBCL/1½-5 for children from 18 months to 5 years 11 months and CBCL/6-18 for children 6 years and older) (subjects enrolling from SP847 or another applicable LCM pediatric clinical study in epilepsy)
- Bayley-III scales for children <18 months of age enrolled in English-speaking countries (subjects enrolling from SP847 or another applicable LCM pediatric clinical study in epilepsy)

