#### **8.4.6 Assessment of suicidality**

Suicidality will be assessed by trained study personnel using the C-SSRS (Columbia University Medical Center, 2008). For subjects  $\geq 6$  years of age, this scale will be used for screening as well as to assess suicidal ideation and behavior that may occur during the study. The C-SSRS will be completed according to the tabular schedule of study procedures, [Section 16.1](#).

Subjects enrolling directly who are  $\geq 6$  years of age will complete the "Baseline/Screening" version of the C-SSRS at Visit 1 and will complete the "Since Last Visit" version at subsequent

visits. If a subject becomes 6 years of age during the study, the “Already Enrolled” version of the C-SSRS should be used at the first visit at which the subject is 6 years of age and the “Since Last Visit” version used at subsequent visits.

The C-SSRS is not validated and will not be used for subjects <6 years of age. Subjects should be monitored for any changes in mood, ideas, or behavior for warning signs of depression. The investigator should be aware of common warning signs that might be a signal for risk of depression. For common signs and symptoms of depression in children younger than 6 years old, reference should be made to the current version of the Diagnostic and Statistical Manual of Mental Disorders. Parents and caregivers should also be advised accordingly and effort should be made at clinic visits to specifically assess potential depression.

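### Section 4.3.3 requires neither withdrawal nor mental-health referral when a child with a Screening C-SSRS attempts suicide on study and answers 'No' to Questions 4 and 5

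*Protocol*

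**What the plan says.** Three criteria in Section 4.3.3 deal with suicidality.

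- **Mandatory criterion 11** concerns attempts. It opens "For subject who did not complete a C-SSRS at Screening, subject has a lifetime history", counts attempts before entry and since study start, and requires withdrawal and immediate referral. Its wording ties the attempt to one form of the scale: "aborted attempt) of the screening version of the C-SSRS".
- **Mandatory criterion 12** covers all subjects aged 6 or older, "regardless of whether or not a C-SSRS was completed at Screening, subject has actual suicidal ideation as indicated by a positive response" to Question 4 or 5 of the since-last-visit version. The subject must be withdrawn and should be referred immediately.
- **Optional criterion 5** is again limited to subjects without a Screening C-SSRS and concerns ideation in the past 6 months. Referral is compulsory; withdrawal is left to clinical judgement.

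Two other places bear on these rules. Exclusion criterion 3 (Section 4.3.2) bars a subject aged 6 or older who "has a lifetime history of suicide attempt (including an actual attempt, interrupted attempt, or aborted attempt"), and lists Question 4 or 5 ideation as a separate ground. Section 8.4.6 says of the C-SSRS that "this scale will be used for screening as well as to assess suicidal ideation and behavior that may occur during the study", but attaches no action to a finding of suicidal behavior.

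**The concern.** The protocol treats attempt and ideation as separate grounds at entry and assesses both during the study. For a child who completed the C-SSRS at Screening, though, it attaches an automatic on-study consequence to ideation only.

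Read literally, the order of severity is reversed. Question 4 or 5 ideation takes a screened child off study with a referral. An actual attempt without endorsed ideation does neither automatically, although a past attempt would have kept the same child out. This is an action rule in a paediatric safety section. Where it is silent, sites must handle an attempt case by case, and nothing in writing obliges them to refer the child.

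**Working it through.** No arithmetic applies. The check is to take each suicidality case in turn and see which rule in Section 4.3.3 responds.

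| Case | Rule that applies | Withdrawal | Referral |
|---|---|---|---|
| No Screening C-SSRS, attempt before entry | Mandatory 11 | Required | Required |
| No Screening C-SSRS, attempt on study | Mandatory 11 by its 'since study start' wording, though tied to the screening version | Required on the evident intent | Required on the evident intent |
| No Screening C-SSRS, Question 4 or 5 ideation in past 6 months (screening version) | Optional 5 | Judgement | Required |
| Any subject aged 6 or older, Question 4 or 5 'Yes' since last visit | Mandatory 12 | Required | Stated (should) |
| Screening C-SSRS completed, aged 6 or older, attempt on study, Questions 4 and 5 'No' | None | Not automatic | Not stated |

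In the last row, criterion 11 fails on population because the child has a Screening C-SSRS. Criterion 12 fails on its trigger because neither question is answered 'Yes'. Optional criterion 5 fails on both.

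The remaining routes for that row are:

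1. Mandatory criterion 1: an adverse event that the investigator considers intolerable and incompatible with continuing.
2. Mandatory criterion 8: the investigator decides that withdrawal is in the child's best interest.
3. Optional criterion 1: a change in psychiatric condition that the investigator thinks warrants stopping.
4. Mandatory criterion 2: a request from the sponsor or a regulator. An attempt judged serious under Section 8.2.1 reaches the sponsor within 24 hours (8.2.4) and falls under ongoing Study Physician review (8.1.9), which could prompt such a request. Suicide attempt is not among the adverse events of special interest in 8.2.2, so this route depends on the event being classed as serious.

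All four can end in withdrawal. None is triggered by an attempt as such, and none states a duty to refer.

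Who counts as screened is not fully settled. Section 5.1 and exclusion criterion 3 place the C-SSRS at Screening for direct enrollees. Section 8.4.6 has those aged 6 or older complete the Baseline/Screening "version of the C-SSRS at Visit 1 and will complete the" since-last-visit version afterwards. Rollover subjects have no Screening Visit; for them Section 5.3 says that "eligibility will be determined on the basis of the inclusion/exclusion criteria and the results of the following assessments", and that list includes the C-SSRS. A child who turns 6 on study gets the Already Enrolled form: that "version of the C-SSRS should be used at the first visit at which the subject is 6 years of age". The last row therefore applies most clearly to direct enrollees when Section 5.1 is followed.

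**The case against.** The strongest reply is that the case is narrow. It needs an attempt together with 'No' to both ideation questions over the same interval. Many attempts would probably bring a 'Yes' and so trigger criterion 12. The protocol does not reproduce the questions, so how often the two diverge cannot be judged from it. This stands, and it limits the size of the point.

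Second, if a site follows Section 8.4.6 and first gives the scale to direct enrollees at Visit 1, those children arguably have no Screening C-SSRS, and criterion 11 would cover them. This also stands as a reading, though 5.1 and exclusion criterion 3 make the other one more natural. It does not remove the gap for any child counted as screened, and it leaves sites unsure whom criterion 11 covers.

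Third, three of the fallback criteria are on the mandatory list. The C-SSRS is also repeated at Titration Visits and clinic visits, and at Unscheduled Visits prompted by an adverse event (5.18). A reader might infer that an attempt could pass undetected, or that the investigator would be powerless to act. The documents do not support that: detection and authority are both in place. What is missing is an automatic consequence and a written referral duty.

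A reader might also infer that criterion 11 fails for on-study attempts by unscreened children because it cites the screening version. Its 'since study start' wording shows the intent to cover them, so this is a drafting ambiguity and not a second gap.

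**Conclusion.** The point holds in a narrow form. Section 4.3.3 gives no automatic withdrawal and no mental-health referral for an on-study actual, interrupted or aborted attempt by a child aged 6 or older who completed a C-SSRS at Screening and answers 'No' to Questions 4 and 5.

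It rests on two assumptions: that criteria 11 and 12 are applied as written, and that direct enrollees complete the C-SSRS at Screening as Section 5.1 says. The number of children affected cannot be derived, because the protocol gives neither the frequency of attempts nor how often one occurs without endorsed ideation. It is probably small. It would be tempting to size the gap by the number of children planned for direct enrolment, but that count says nothing about how many would meet this combination, and it includes children under 6, who do not take the scale.

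The change is still worth making: the rule concerns the safety of children, its coverage departs from the protocol's own entry rule, and correcting it costs little.

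**What to change.** Leave criterion 11 as it is, including its reach to attempts since study start. Add one item to the mandatory list in Section 4.3.3, for example:

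> For all subjects, whether or not they completed a C-SSRS at Screening: any actual, interrupted or aborted suicide attempt since study start, identified on any version of the C-SSRS or from an adverse event or other report. The subject must be referred at once to a mental healthcare professional and withdrawn from the study, with LCM tapered as in Section 4.4.1.

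Three features matter. Covering all subjects avoids an age limit that could take away whatever cover criterion 11 now gives younger children. Allowing any source catches an attempt known only from a hospital or adverse event report. Because the item does not depend on screening status, the conflict between Sections 5.1 and 8.4.6 no longer affects how on-study attempts are handled.

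If the sponsor prefers not to force a child off a drug that is helping, the minimum is to make immediate referral compulsory in this case and leave withdrawal to judgement, as optional criterion 5 already does.

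The cost is one clause by amendment and no new assessment. The downside is possibly a few more withdrawals and the loss of investigator discretion in those cases, a loss that criteria 11 and 12 already accept in parallel situations.
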